Assessment and prediction of the effectiveness of anti-IL-5/IL5R inhibitors in a real-world setting: a two-step study

[name] [name]

[name] PhD

CIUSSS du Nord de l'île de Montréal, Hôpital du Sacré-Cœur de Montréal

Université de Montréal

NCT06239441

Scientific rationale

Asthma is a chronic respiratory disease affecting up to 8.4% of Canadians (1). While the majority of asthmatics are controlled with a low dose of inhaled corticosteroids (ICS), there are still approximately 10% of asthmatics who remain uncontrolled despite using high doses of an ICS with additional controllers. These patients are defined as severe asthmatics (2).

Over the past decade, it has become obvious that asthma is a heterogeneous disease that is composed of several phenotypes. The identification of those phenotypes has been associated with the development of biological therapies that specifically target antibodies, cytokines, and their receptors, such as immunoglobulin E, interleukin (IL) -5, and IL-5 receptor or IL-13/IL-4 receptor in the treatment of severe cases of asthma. Interleukin (IL)-5 plays a central role for eosinophil recruitment, activation, and survival. IL-5 and its receptor (IL-5R) have been targeted for developing antagonists against this cytokine or its receptor in the improvement of asthma control. There are three drugs targeting IL-5 or its receptor that have been developed to treat severe eosinophilic asthma: mepolizumab (NucalaTM), reslizumab (CinqairTM), and benralizumab (FasenraTM). Mepolizumab a humanized monoclonal anti-IL-5 (IgG1) antibody was the first IL-5 antagonist to be commercialized in 2016 followed by reslizumab a humanized anti-IL-5 (IgG4/k) antibody. Benralizumab a humanized monoclonal antibody against interleukin 5 receptor α (IgG1 κ) was commercialized in 2018 in the province of Quebec.

Anti-IL-5/IL5R inhibitors have been shown to decrease asthma exacerbations by approximately 50% (3, 4) and allow at least a 50% reduction in the doses of oral corticosteroids in cortico-dependent subjects(5, 6). Their efficacy has been mainly studied in clinical trials including selected populations. The effectiveness of anti-IL-5/IL5R inhibitors on the reduction of asthma exacerbations has rarely been assessed in a real-word setting where the characteristics of the patients receiving this medication differ substantially from the patients that were included in the clinical trials. Data from an Israeli tertiary clinic that followed 61 patients who had received mepolizumab for at least 3 months from 2016 to 2018(7) showed a large reduction of the annual asthma exacerbation rate before (3.14 ± 2.3) and after treatment 0.85 ± 1.1 $p < 0.001$).

However, it was unclear whether or not this study included smokers & ex smokers and the atopic status or the number of patients with a reversible airflow limitation were also not reported. In a

day-to-day practice, smokers and patients with a non-reversible airflow limitation or patients who are not optimally adherent to their asthma medication received mepolizumab, while at the same time were excluded or they represented a small proportion of the patients that were enrolled in the clinical trials.

The reduction of exacerbations has been shown to depend on the level of blood eosinophil counts. Better treatment effects were observed in patients showing high eosinophil counts (≥ 500 eosinophils/ μ L) compared to those with lower blood eosinophil counts. Although anti-IL-5/IL5R inhibitors have a very good response rate, some patients remain uncontrolled in spite of taking this medication(8, 9). Furthermore, although the addition of anti-IL-5/IL5R inhibitors allowed a 50% decrease in the dose of oral corticosteroids (OCS) in steroid-dependent patients, a fair proportion could not be completely weaned from prednisone (5, 6). Beside the baseline level of blood eosinophil counts(10), there is no other clear predictor of response to anti-IL-5/IL5R inhibitors. To our knowledge, no real-world study has ever tried to identify response predictors.

Therefore, it is essential to gather data from the real world to ensure that the response rate is at least as good as in the clinical trials and to identify predictors of response to therapy.

Hypothesis

The majority of patients receiving anti-IL-5/IL5R inhibitors will have at least a 50% decrease in their asthma exacerbations rate in a tertiary clinic specialized in the field of severe asthma.

The level of blood and sputum eosinophils will be the main response predictor to anti-IL-5/IL5R inhibitors in a tertiary clinic specialized in the field of asthma whereas the rate of exacerbation in the year prior to the initiation of anti-IL-5/IL5R inhibitors will be the main predictor of asthma exacerbations in a non-selected population of severe asthmatics in Quebec.

Primary Objectives

1. To assess and compare the response* to treatment before and after the initiation of anti-IL-5/IL5R inhibitors in patients followed in a tertiary asthma clinic from the Province of Quebec and in a non-selected population of asthmatic subjects covered by the *Régie de l'Assurance Maladie du Québec*'s (RAMQ) public drug insurance plan or by a private drug insurance.
2. To assess the clinical response predictors to anti-IL-5/IL5R inhibitors in a cohort of severe asthmatics followed in tertiary care as well as in a non-selected population of asthmatic subjects covered by the RAMQ's public drug insurance plan *or by a private drug insurance*.

* Response to treatment will be defined by a reduction of asthma exacerbations of at least 50% *and* or a 50% or higher reduction of the OCS doses in steroid dependent patient compared to the year prior to treatment initiation.

Secondary objectives:

1. To assess the mean reduction of exacerbation in both cohorts.
2. To assess the adherence and persistence to treatment with anti-IL-5/IL5R inhibitors and ICS after treatment initiation with anti-IL-5/IL5R inhibitors..

Study populations.

A) A Tertiary asthma clinic cohort of patients 18 years and older who are followed at the outpatient asthma clinic of Sacre-Cœur Hospital and who have been treated with anti-IL-5/IL5R inhibitors between January 2016 and June 2020 and are included in the reMed database;

We will ensure that those patients had severe eosinophilic asthma inadequately controlled on high dose ICS plus additional controlled therapy and had a blood eosinophil count of 150 cells/ μ L on initiation or 300 cells/ μ L in the past 12 months and had either 2 or more significant asthma exacerbations in the past 12 months or were treated with daily oral steroids

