A retrospective pre-post anti-IL-5/IL5R inhibitors treatment cohort study using the RESP database and the hospital charts including patients with severe asthma followed at the *Hôpital du Sacré-Coeur de Montréal* (Tertiary asthma clinic cohort).

Another retrospective pre-post anti-IL-5/IL5R inhibitors treatment cohort selected from the Quebec health administrative databases and reMed database (Population-based cohort).

Cohort entry will be defined as the first prescription of anti-IL-5/IL5R inhibitors filled on or after January 1, 2016 for both cohorts.

Outcomes

Objective 1, primary outcome: Response to anti-IL-5/IL5R inhibitors, defined by a reduction of asthma exacerbations of at least 50% and a 50% or higher reduction of the OCS doses in steroid dependent patients in the year following the initiation of anti-IL-5/IL5R inhibitors compared to the year prior to treatment initiation, in the tertiary asthma clinic cohort and in the population-based cohort.

Objective 1, secondary outcomes: Exacerbation rates and OCS doses (for steroid-dependent patients) in the year preceding and following initiation of anti-IL-5/IL5R inhibitors in the tertiary asthma clinic cohort and in the population-based cohort.

Objective 2: Response to anti-IL-5/IL5R inhibitors in the tertiary asthma clinic cohort and in the population-based cohort in the year following initiation of anti-IL-5/IL5R inhibitors.

Potential Predictors

Potential clinical response predictors to anti-IL-5/IL5R inhibitors in the Tertiary asthma clinic cohort are: age, sex, atopy, body mass index, smoking habits, percent predicted FEV₁, asthma treatment prescribed, blood eosinophil count, and sputum eosinophil count at cohort entry.

Potential clinical response predictors to anti-IL-5/IL5R inhibitors in the Quebec population (Population-based cohort) are: age, sex, type of asthma treatment filled in the year before treatment initiation with anti-IL-5/IL5R inhibitors adherence to ICS in the year before and after treatment initiation with anti-IL-5/IL5R inhibitors, exacerbation rate in the year before treatment initiation with anti-IL-5/IL5R inhibitors, and socio economic status (welfare recipients).

Source of data

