The RAMQ database is formed of three files containing information on the patients' characteristics, medical services and prescribed medications. The RAMQ Patient file contains the patient's healthcare insurance number (HCIN), which is a unique patient identifier, and information on age, sex, birth date, area of residence, type of drug insurance plan, and date of death, if relevant. This file covers all Quebec residents. The RAMQ Prescription Medications file contains the HCIN and claims data on prescriptions filled at community pharmacies; for example, name, dose, form, quantity of medication dispensed, date & duration of the prescription, cost of medications, as well as the identification and the specialty of the prescribing physician for Quebec residents covered under the RAMQ's Public Drug Insurance Plan, about 42% of the population; these include persons receiving social assistance, persons not covered by a private drug plan, and about 90% of elderly. This file also contains the dates of coverage under the RAMQ's Public Drug Insurance Plan. The RAMQ Medical Services file contains the HCIN and claims data on medical services dispensed on a fee for service to all residents of Quebec in hospitals, emergency departments (ED) or medical clinics. Physicians are reimbursed through RAMQ by submitting claims for medical services provided. This file contains the date of service, where the service was dispensed, one diagnosis coded with ICD-9, medical procedures provided,

cost of the service, as well as, specialty and identification of the treating physician. These databases can be linked between one and another using the HCIN.

The MED-ECHO database contains information on all admissions to acute care hospitals in Quebec. It contains the HCIN, the date of admission, length of stay, and diagnoses coded with ICD-9/ICD-10 codes; admission and principal & secondary diagnoses. The RAMQ and MED-ECHO databases can also be linked using the HCIN.

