The reMed database contains data on medications dispensed in community pharmacies to a sample of patients with private drug insurance. The reMed contains the HCIN, the private insurance policy number (PIPN), the type of insurance plan (co-payment, annual premium, and so on), the name, dose formulation and quantity of the medication dispensed, the date the medication was dispensed, the pharmacy & the prescriber's encoded identifier, the cost of medications, and the amount reimbursed by the insurer. The drug related variables recorded in reMed are almost identical to the variables recorded in the RAMQ Prescription Medications file. The HCIN allows the linkage of the reMed to the RAMQ and MED-ECHO databases.

Methods

After having obtained the authorization from the research ethics committee of the CIUSSS du Nord-de-l'île-de-Montréal and from the director of Professional Services, all the charts of patients who received anti-IL-5/IL5R inhibitors at the tertiary asthma clinic of *the Hôpital du Sacré-Coeur de Montréal* will be reviewed.

A response to treatment will be defined by a 50% reduction in the number of asthma exacerbations in the year following the initiation of anti-IL-5/IL5R inhibitors compared to the year preceding the initiation of the treatment or a 50% decrease in the OCS doses for steroid dependent patients.

A functional response to treatment will also be assessed in the Tertiary asthma clinic cohort. An improvement of FEV₁ of 12 % and ≥ 200 ml will be considered as clinically significant.

Asthma exacerbations will be defined by a short treatment with systemic corticosteroids (less than 14 days), visit to the emergency department or hospitalization related to asthma. If two markers of an asthma exacerbation occurred with 14 days, they will be counted as only one exacerbation. This definition will be applied in the Tertiary asthma clinic cohort and the population-based cohort.

The potential predictors of response to treatment will be collected in the Quebec registry in respiratory health (RESP) database and or the medical charts: age (continuous), sex (women/men), atopy (atopic/non atopic), body mass index (continuous), smoking habits (current or ex/never smokers)(never/ever/current), percent predicted FEV₁, asthma treatment (dose of ICS, dose of OCS if any), exacerbation rate in the year preceding treatment initiation, blood eosinophil count, and sputum eosinophil count.

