The Quebec Registry in Respiratory Health (RESP) is a database originally built in 2010 by [name]. This registry aims to store clinical and functional data in subjects with asthma and COPD followed at the *Hôpital du Sacré-Coeur de Montréal* or at the *Centre Hospitalier Universitaire de Sherbrooke*. The patients included in the database have also consented to have their clinical data matched to the *Régie de l'assurance médicale du Québec* (RAMQ) and *Maintenance et exploitation des données pour l'étude de la clientèle hospitalière* (MED-ECHO) administrative databases and the reMed database on medications for patients with private health insurance plans which enables access to data on medical services, hospitalisations and medications dispensed by pharmacies. This databases allows us to collect the following variables: age, sex, area of residence (rural or urban), treatment (if insured with the RAMQ), comorbidities, visits to the physician for asthma and all causes, visits to the emergency for asthma and any other medical issues, and hospitalization for asthma and any other medical issues.

This database allows us to assess the adherence to inhaled corticosteroids (ICS) by calculating the proportion of days covered (PDC) (11), a measure of adherence based on prescription claims data. The PDC is defined as the sum of the duration of all prescriptions of ICS filled over one year, divided by 365 days, expressed in percentages. The PDC will be estimated using prescription refill

data obtained from the RAMQ and reMed databases in the year preceding and following cohort entry.

Potential response predictors to treatment will also be collected in the RAMQ and reMed databases: age (continuous), sex (women/ men), type of asthma treatment (ICS, long-acting beta 2 agonists (LABA), Long-acting muscarinic antagonists (LAMA), Leukotriene-receptor antagonist (LTRA), omalizumab, or OCS if any), adherence to asthma treatment before and after cohort entry, comorbidities as measured by the Charlson score before and after cohort entry, exacerbation rate in the year preceding cohort entry, and area of residence (rural or urban) at cohort entry.

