We shall require the authorization from *the Commission d'accès à l'information du Québec* to obtain the RAMQ and MED-ECHO data on healthcare utilization and medication for all subjects who have been diagnosed with asthma and who have been receiving anti-IL-5/IL5R inhibitors between January 2016 and June 2020; for example, subjects included in the tertiary asthma clinic cohort and the population-based cohort.

We will require from the RAMQ and MED-ECHO, the data on visits to the physicians, visits to the emergency departments, and hospitalizations for asthma and any other medical issues as well as the use of medication of all patients who have been diagnosed with asthma as defined by a validated operational definition(12) – 2 ambulatory visits for asthma or an hospitalization for asthma within the past 2 years a – in the year preceding the prescription of anti-IL-5/IL5R inhibitors and who have been receiving anti-IL-5/IL5R inhibitors from January 2016 to June 2020 in the Province of Quebec. We will request the data from January 2014 to June 2021.

Statistical analysis

We will estimate the proportion and confidence interval of patients' responder to anti-IL-5/IL5R inhibitors in the Tertiary asthma clinic cohort and the population-based cohort.

A logistic regression model will be used to identify the response predictors to anti-IL-5/IL5R inhibitors. Variable selection will be made with the Lasso selection procedure (13).

We will perform a Poisson regression model to compare the exacerbation rate in the year before and after the treatment initiation with anti-IL-5/IL5R inhibitors in the tertiary asthma clinic cohort and the population-based cohort. We will include all patients who received anti-IL-5/IL5R inhibitors in the analysis. The duration of follow-up will be taken into account using an offset in the Poisson regression model.

We will perform a linear regression model to compare the OCS doses in the year before and after the treatment initiation with anti-IL-5/IL5R inhibitors in the tertiary asthma clinic cohort and the population-based cohort.

Sample size and statistical power

To fulfill the primary objective

With 60 patients in the Tertiary asthma clinic cohort and an expected response rate of 50% we will have the power to identify 6 predictors (14). With 570 patients in the population-based cohort and an expected response rate of 50% we will have the power to identify more than 50 predictors (14).

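### The planned predictor models cannot support the hypothesised contrast between cohorts: eosinophils are never a candidate in the population, and the two clinic lists disagree on prior exacerbation rate

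*Combined protocol and SAP*

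**What the plan says.** The second paragraph under Hypothesis sets two statements against each other. In the clinic, "The level of blood and sputum eosinophils will be the main response predictor to anti-IL-5/IL5R inhibitors in a tertiary clinic". In the population, "whereas the rate of exacerbation in the year prior to the initiation of anti-IL-5/IL5R inhibitors will be the main predictor of asthma exacerbations".

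The candidate predictors are listed twice, under Potential Predictors and again under Methods.

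- **Clinic, Potential Predictors:** the list ends "asthma treatment prescribed, blood eosinophil count, and sputum eosinophil count at cohort entry". Prior-year exacerbation rate is not in it.
- **Clinic, Methods:** the variables to be taken from the RESP registry or charts include "exacerbation rate in the year preceding treatment initiation, blood eosinophil count, and sputum eosinophil count".
- **Population, Potential Predictors:** the list includes "exacerbation rate in the year before treatment initiation with anti-IL-5/IL5R inhibitors, and socio economic status (welfare recipients") but no eosinophil measure.
- **Population, Methods:** the list ends "exacerbation rate in the year preceding cohort entry, and area of residence (rural or urban) at cohort entry", again with no eosinophil measure.

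Source of data describes RAMQ as "three files containing information on the patients' characteristics, medical services and prescribed medications", MED-ECHO as hospital admissions, and reMed as dispensed drugs. Laboratory results are mentioned in none of them.

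Under Statistical analysis, "A logistic regression model will be used to identify the response predictors to anti-IL-5/IL5R inhibitors", with Lasso selection. The section does not define a main predictor, set a predictor list common to both cohorts, or compare predictors between cohorts. The only item under Limitations is the small privately insured sample.

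**The concern.** A claim that one factor leads in one cohort and another factor leads elsewhere needs both factors to be eligible in both places. Here eosinophils are never eligible in the population. On the Potential Predictors lists, prior rate is not eligible in the clinic either. The study could then report that eosinophilic inflammation drives response in specialist care and past exacerbations drive it in the wider population, when prediction is the same in both.

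Two further problems affect the same claim. The clinic finding can change with the list used, and the plan does not say which list governs. The halves also name different outcomes, response in the clinic and exacerbations in the population, while Objective 2 under Outcomes and the logistic model use response in both. All of this bears on the second primary objective.

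**Working it through.** The plan gives no figure to reproduce. The main check is a comparison of the lists; the simulations only illustrate its size.

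**1. Eligibility of each hypothesised main predictor**

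| Model | Eosinophils | Prior exacerbation rate |
|---|---|---|
| Clinic, Potential Predictors | yes | no |
| Clinic, Methods | yes | yes |
| Population, Potential Predictors | no | yes |
| Population, Methods | no | yes |

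The population half is structural under either list. The clinic half is structural only under Potential Predictors.

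**2. How often the contrast appears when prediction is identical**

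Inputs from the plan (Sample size and statistical power; Target enrolment): clinic n = 60 for the predictor analysis, or 100 as the enrolment target; population n = 570; 50% response. Assumed, because the plan gives none: effect sizes, correlations, and the rule for ranking first. The same logistic model generates both cohorts, logit P(response) = b1 × eosinophils + b2 × prior rate, on standardised variables, with all other candidates null. The contrast counts as found if eosinophils rank first in the clinic and prior rate ranks first in the population.

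*Design A.* Ranking by largest |z|; log odds ratios per SD of 0.4 and 0.7 (odds ratios exp(0.4) = 1.49 and exp(0.7) = 2.01), assigned either way; correlation 0 to 0.3; clinic n = 60 to 100.

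| Stronger factor | Potential Predictors lists | Methods clinic list |
|---|---|---|
| Prior rate | about 37-79% | about 17-24% |
| Eosinophils | about 69-91% | about 59-74% |

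Repeat runs move the ends of these ranges by a few points.

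*Design B.* Ranking by first variable to enter the Lasso path; separate blood and sputum markers with correlation 0.5; 4,000 runs per row. Cells are clinic n = 60, with n = 100 in brackets.

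| Odds ratio per SD, eosinophils / prior rate | Potential Predictors lists | Methods lists | Both factors eligible in both cohorts (hypothetical) |
|---|---|---|---|
| 2.5 / 1.5 | 86% (96%) | 80% (91%) | 0% (0%) |
| 2.0 / 1.5 | 74% (88%) | 65% (77%) | 0.8% (0.9%) |
| 2.0 / 2.0 | 72% (88%) | 46% (50%) | 24% (25%) |
| 1.5 / 2.0 | 46% (57%) | 21% (17%) | 21% (17%) |
| 1.0 / 2.0 | 21% (20%) | 6% (2%) | 6% (2%) |
| 2.0 / 1.0 | 7% (8%) | 7% (8%) | 0% (0%) |
| 1.0 / 1.0 | 2% (2%) | 2% (2%) | 2% (2%) |

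A smaller run with cross-validated Lasso (300 runs, n = 60, odds ratios 2.5 / 1.5, effect shared by the two eosinophil markers) gave 53%, 48% and 6% for the three columns.

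When eosinophils are the stronger factor, the Methods list lowers the false contrast only modestly, because the remaining cause is their absence from the population model. When prior rate is stronger, the Methods list brings it down to the common-list level.

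**3. Prior rate is built into the outcome**

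Response on exacerbations means a post-treatment count of at most half the pre-treatment count. Give every patient the same rate, 1.48 a year (the plan's planning value), and the same halving to 0.74. No patient then truly responds better than another. The chance of being a responder, by prior count, is:

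- 2 prior events: P(post ≤ 1) = exp(-0.74) × (1 + 0.74) = 0.477 × 1.74 = 0.83
- 4 prior events: P(post ≤ 2) = 0.477 × (1.74 + 0.74²/2) = 0.477 × 2.014 = 0.96
- 6 prior events: P(post ≤ 3) = 0.477 × (2.014 + 0.74³/6) = 0.477 × 2.081 = 0.99

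The trend is regression to the mean. With between-patient variation in the underlying rate (gamma-Poisson), a uniform 50% reduction and no true predictor, prior rate still shows a log odds ratio of about 0.1-0.8 per SD. Prior rate leading in the population is therefore weak evidence about who benefits.

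**The case against.** **No between-cohort test is planned.** Primary objective 2 assesses predictors in each cohort separately, and the lists are openly labelled by cohort. This stands: it is a problem of what may be concluded, and no planned test is wrong. But the hypothesis itself is worded as a contrast, and Perspective promises an answer in both populations.

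**The Methods clinic list is the more detailed and may be meant to govern.** This also stands. If it governs, the two factors compete fairly in the clinic, and much of the artefact goes when prior rate is the stronger. It does nothing for the population half.

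**The simulations use one outcome, whereas the hypothesis names two.** This is correct, so the percentages do not measure the hypothesis as literally worded. The mismatch is itself a defect, because the only predictor model planned is for response.

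**The percentages are illustrative.** They depend on assumed effects, null companions and a ranking rule. Path entry and cross-validated Lasso gave 86% and 53% in closely similar settings. The comparison of the lists depends on none of this.

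A reader might infer that the lists alone settle the result in advance. The documents do not support that. Another candidate can rank first, the Methods list lets prior rate win in the clinic, and the contrast appears in only about 2% of runs if nothing predicts and 7-8% if only eosinophils do.

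**Conclusion.** The point holds as an interpretive defect in the second hypothesis. Eosinophils cannot lead in the population model under any list, the clinic conclusion turns on two unreconciled lists, and the halves name different outcomes. If both factors predict equally well in both cohorts as assumed in Design A, a false contrast appears in about 37-91% of studies with the Potential Predictors lists. With the Methods clinic list it appears in about 17-24% (prior rate stronger) or 59-74% (eosinophils stronger). The sizes rest on the stated assumptions; the structural finding does not.

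It is also tempting to conclude that a head-to-head comparison of eosinophils with prior rate in the clinic would settle the question. It would not. Prior rate is tied to the outcome by definition. In a small check (60 runs per scenario, log odds ratios 0.7 and 0.4 either way), a 95% bootstrap interval for the difference in loss of fit included zero in 87-95% of runs at n = 60 and 77-93% at n = 100.

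**What to change.** 1. Reconcile the two clinic lists by adding prior-year exacerbation rate to the one under Potential Predictors. Methods already provides for collecting it.
2. Use response as the outcome in both halves of the hypothesis. Reword the population half as the main predictor among the variables available in claims, and drop the contrast between cohorts.
3. For any between-cohort statement, refit both cohorts on the same full set of shared variables: age, sex, asthma treatment, ICS adherence before entry, comorbidity, area of residence and prior exacerbation rate. Methods describes consent to claims linkage for registry patients and a data request covering both cohorts.
4. State that prior rate is the baseline of the response definition, so its association with response partly reflects regression to the mean. Report any ranking of eosinophils against prior rate in the clinic as exploratory, with its uncertainty.

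The cost is protocol wording, one extra model fit, one more candidate term in a small clinic model, and a narrower claim for the population cohort. No new data collection is needed.
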